10. STATISTICAL CONSIDERATIONS

10.1 Study Endpoints, Analysis Sets, and Covariates

10.1.1 Study Endpoints

10.1.1.1 Primary Endpoint

PFS defined as time from randomization until disease progression or death from any cause. Response and disease progression determined by a blinded Independent Review Committee (IRC).

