$$OS = (\text{death date} - \text{randomization date} + 1) / 30.4$$

Subjects still alive will be censored at the date last known to be alive. If the date last known to be alive is after the date that triggers the analysis (ie, the data cutoff date), the subject will be censored at the analysis trigger date.

Progression-Free Survival (PFS)

PFS time will be calculated from the time of randomization (in months) until PD or death due to any cause, whichever occurs first:

$$PFS = (\text{PD} / \text{death date} - \text{randomization date} + 1) / 30.4$$

The duration of PFS will be right censored for subjects who meet any of the following conditions: 1) no baseline / **post-baseline** disease assessments; 2) starting a new anti myeloma therapy before documentation of progressive disease or death; 3) progressive disease or death immediately after more than 70 days without disease assessment visit or; 4) alive without documentation of disease progression before the

analysis trigger date; **5) lost to follow up or withdrawn consent.** The censoring rules for PFS primary analysis are described in [Table 1](#). These rules are based on the May 2007 FDA Guidance for Industry, ‘Clinical Trial Endpoints for the Approval of Cancer Drugs and Biologics’ (<https://www.fda.gov/ucm/groups/fdagov-public/@fdagov-drugs-gen/documents/document/ucm071590.pdf>).

Table 1. Censoring Rules for Primary PFS Analysis

Situation	Date of Progression or Censoring	Outcome
No baseline / post-baseline disease assessments	Date of randomization	Censored
New anti-myeloma treatment started before documentation of PD or death	Date of last disease assessment prior to start of a new anti-myeloma treatment	Censored
Death or PD immediately after more than 1 consecutively missed disease assessment visit*	Date of last disease assessment visit before the first missed visit	Censored
Alive and without PD documentation	Date of last disease assessment	Censored
Lost to follow up or withdrawn consent	Date of last disease assessment	Censored
Death or PD between planned disease assessments	Date of death or first disease assessment showing PD, whichever occurs first	Progressed
Death before first disease assessment	Date of death	Progressed

* If death or PD is more than 70 days after previous disease assessment, or randomization date if there is no previous disease assessment

Randomization Date

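### SAP Table 1 can both censor and count as a PFS event a death within 70 days with no post-baseline assessment, if its first row applies when either assessment is missing

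*SAP*

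**What the plan says.** The protocol (Section 10.1.1.1) gives the endpoint: "PFS defined as time from randomization until disease progression or death from any cause". SAP Section 2.1 repeats it.

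The censoring rules are in SAP Section 5, under Progression-Free Survival and in Table 1. The lead-in reads: "The duration of PFS will be right censored for subjects who meet any of the following conditions". The parts that matter here are:

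- **Condition 1 and Table 1, row 1.** A subject with "no baseline / post-baseline disease assessments" is censored at the date of randomization. Nothing restricts this to living subjects.
- **Table 1, row 4.** "Alive and without PD documentation" is censored at the last assessment. This row, like condition 4, does carry the restriction.
- **Table 1, missed-visit row.** "Death or PD immediately after more than 1 consecutively missed disease assessment visit" is censored, at this date: "Date of last disease assessment visit before the first missed visit". The footnote defines the case: "If death or PD is more than 70 days after previous disease assessment, or randomization date if there is no previous disease assessment".
- **Table 1, last row.** "Death before first disease assessment" has the date of death as its date and counts as an event. No time limit is given.

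No order of precedence appears in the visible text. The code in SAP Appendix B is redacted, so a rule stated there cannot be seen.

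**The concern.** One primary-endpoint death can be given two outcomes. Two programmers working from the same page could code it differently and each point to a row in support. One of the outcomes removes early deaths from an endpoint that counts death from any cause.

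The investigator-assessed and ORCA analyses in SAP Table 3 follow the same method as the primary analysis, so they inherit the ambiguity. None of the PFS sensitivity analyses listed there is directed at deaths before the first post-baseline visit.

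**Working it through.** **1. Who meets both rules.** In the last row, the first disease assessment must mean the first one after baseline. Measurable disease is an entry requirement (Protocol 4.1, criterion 103), and M-protein or light-chain results must be available before randomization (Protocol 7.3.21.1).

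| Unassessed death | Row 1, slash = either missing | Row 1, slash = both missing | Missed-visit row and footnote | Last row |
|---|---|---|---|---|
| Up to day 70 | censored at randomization | almost no one qualifies | does not apply | event |
| After day 70 | censored at randomization | almost no one qualifies | censored | event (no limit stated) |

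The first line holds the main conflict, and it depends on the slash. In condition 1 the term post-baseline is set in bold, which the SAP appears to use for added text. A missing post-baseline assessment then looks like a separate ground for censoring, so either missing is the likelier reading.

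**2. What was probably meant.** The footnote starts the 70-day clock at randomization when there is no earlier assessment. That clause would do nothing if row 1 already censored all such deaths, and the last row would be nearly empty. Every row has effect only if row 1 covers subjects with neither progression nor death, the last row covers unassessed deaths up to day 70, and the missed-visit row covers later ones. This also fits the endpoint definition.

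**3. Design figures.** With 188 events and 2:1 allocation, V = 188 × (2/3) × (1/3) = 41.78 and √V = 6.464. The critical HR is exp(−1.96/6.464) = 0.738, as the SAP states. At HR 0.6, z = ln(0.6) × 6.464 = −3.30 and power is 91.0%, in line with the stated minimum of 90%.

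**4. How many subjects.** The documents give no early-death rate. Assumption: a constant death hazard, equal in both arms, from the 47.6-month median OS that Protocol 2.5.4 quotes for Kd in an earlier trial. Then p = 1 − exp(−ln 2 × (d/30.4)/47.6), where d is the day of the first post-baseline visit. Visits are due 28 ± 7 days from cycle 1 day 1. First dosing is allowed up to 3 days after randomization (Protocol 5.1) or 5 days (SAP Section 5).

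| First visit | p | Expected deaths, 450 × p | Share of 188 events |
|---|---|---|---|
| Day 21 (earliest, dosed on day of randomization) | 0.0100 | 4.5 | 2.4% |
| Day 28 (on schedule) | 0.0133 | 6.0 | 3.2% |
| Day 38 (35 + 3) | 0.0180 | 8.1 | 4.3% |
| Day 40 (35 + 5) | 0.0190 | 8.5 | 4.5% |

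Half the hazard at day 21 gives p = 0.0050, or 2.3 deaths. Double the hazard at day 40 gives p = 0.0376, or 16.9 deaths.

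**5. Effect on the test.** If a KdD deaths and b Kd deaths are censored at randomization and the analysis still waits for 188 events, z moves toward KdD by about (a/3 − 2b/3)/6.464.

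- A 2:1 split such as 6 and 3 gives (2 − 2)/6.464 = 0.
- Under equal risk the variance of the numerator is (300/9 + 4 × 150/9) × p(1−p) = 100 × p(1−p), so the SD of the shift is 10√(p(1−p))/6.464. This is 0.11 at p = 0.0050, 0.15 at 0.0100, 0.21 at 0.0190 and 0.29 at 0.0376.
- In 400,000 simulated binomial draws, the central 95% of shifts ran from −0.41 to +0.41 at p = 0.0190 and from −0.62 to +0.57 at p = 0.0376.
- At HR 0.6, the most adverse of these limits leaves z = −3.30 + 0.62 = −2.68, still beyond −1.96. At HR 0.738, z = ln(0.738) × 6.464 = −1.96, so any adverse shift would matter.

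Illustration near the threshold, with the cutoff held fixed: HR 0.72 on 178 events has 1-sided p = 0.019. Adding 10 early deaths split 7 to 3 (KdD to Kd) gives HR 0.739 and p = 0.025.

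**The case against.** The strongest reply is that Table 1 has one sensible reading, set out in step 2 of the working, and that the list of conditions is shorthand for the table. Condition 5 supports this: taken literally, it would censor a subject who withdrew consent after documented progression. This part stands. It makes the defect a missing qualifier in condition 1 and row 1, not a dispute about intent. It does not remove the defect, because the lead-in censors on any one condition, and row 4 shows that the authors wrote the restriction where they wanted it.

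Three stronger readings are tempting, and the documents do not support them.

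- **A reader might infer that the conflict is unconditional.** It depends on the slash. If row 1 needs both assessments to be missing, the entry requirements leave almost no one in it.
- **A reader might infer that deaths after day 70 are equally contested.** The footnote names the case with no previous assessment and points to censoring. Two gaps remain: the last row does not mention the 70-day limit, and the missed-visit row gives no usable date when there is no post-baseline visit.
- **A reader might infer that such a subject could be censored at a screening sample, before randomization.** That requires a baseline sample to count as a disease assessment, which would empty the last row.

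Early deaths are also not hidden from the report. OS censors only subjects still alive, and SAP Section 9.6.2 lists all on-study deaths. Neither shows PFS under the other rule.

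**Conclusion.** The point holds as a minor inconsistency in the visible text. On the likelier reading of the slash, condition 1 and row 1 censor deaths within 70 days of randomization that the last row counts as events. The censoring side is the one that is wrong as written.

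Under the stated hazard assumption, about 4.5 to 8.5 of 450 subjects would be affected, or roughly 2 to 17 with the hazard halved or doubled. The true count could lie outside this range, because the rate is borrowed from another trial and early hazard need not be constant. With equal risk in both arms the expected z shift is 0, with an SD of about 0.1 to 0.3.

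A reader might infer that the primary result is biased or unsafe. The documents do not support that. The direction of any effect is unknown, a result at the design HR of 0.6 would not change, and only one near 0.738 could.

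**What to change.** 1. Limit condition 1 and row 1 of Table 1 to subjects with neither progression nor death.
2. State in the last row that it applies to deaths within 70 days of randomization with no post-baseline assessment. State that later unassessed deaths follow the missed-visit row and are censored at the randomization date, which row 1 already uses.
3. The Amendment 6 rationale in the protocol says that the primary endpoint has been met. The sponsor should therefore state which rule was programmed and how many subjects it affected in each arm. If the number is not zero, show the stratified log-rank result under the other reading.

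The cost is a few lines of SAP wording, one count by arm and at most one rerun of the primary analysis. No new data are needed.

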6.1 Full Analysis Set (Intent-to-Treat (ITT) Population)

The full analysis set will include all randomized subjects. All subjects will be analyzed according to treatment to which they are randomized. Full analysis set will be used for the primary and key secondary endpoints

6.2 Safety Analysis Set

The safety population will include all randomized subjects who received at least 1 dose of any study treatment (ie, carfilzomib, dexamethasone, or daratumumab). Subjects in the analyses based on the safety analysis set will be analyzed according to the treatment group corresponding to the actual treatment received.

6.3 Per Protocol Set(s)

The per protocol analysis set is a subset of the full analysis set which includes subjects who do not have important protocol deviations that are considered to have an effect on efficacy outcomes. The list of important protocol deviations is maintained by the sponsor on an ongoing basis and will be finalized before the primary analysis of the study. **The Per-protocol Sets are different for OS analysis from PFS/ORR analysis.**

Subjects with the following protocol deviations will be excluded from the per protocol set for OS analysis:

- **PP** - Inclusion criteria of relapsed or progressive multiple myeloma
- **PP** - Inclusion criteria of measurable disease
- **PP** - Inclusion criteria of at least PR to at least 1 prior line of therapy
- **PP** - Inclusion criteria of 1 - 3 prior therapies for multiple myeloma
- **PP** - Inclusion criteria of prior exposure to carfilzomib therapy
- **PP** - Inclusion criteria of prior exposure to anti-CD38 antibody therapy
- **PP** - Exclusion criteria of history of other malignancy within the past 5 years
- **PPD** - Subject received therapy with a marketed or investigational anticancer therapeutic or radiation to large marrow reserves for either a therapeutic or palliative intent prior to confirmed progressive disease
- **PP** - Subject received different treatment type from randomized treatment assignment; subject in arm 2 received daratumumab
- **PP** - Incorrect carfilzomib dose (under dose)

In addition to the deviations listed above, subjects who had the following deviations will also be excluded from per-protocol set for PFS and ORR analyses:

- **PPD** - Subject permanently discontinued treatment due to progressive disease (PD) based on local labs not central labs, except in the case of disease progression based on hypercalcemia
- **PP** - Screening lab disease assessment performed outside window and not reported prior to C1D1 dosing, such that the primary endpoint cannot be assessed

- **PPD** - Failure to obtain extramedullary plasmacytoma assessment and/or bone lesion assessment not carried out within 30 days prior to randomization or not obtained post-randomization and prior to C1D1 such that the primary endpoint cannot be assessed
- **PPD** - Failure to obtain all required response assessments per protocol schedule of assessments and IMWG URC specifications to assess PFS

6.4 MRD Evaluable Analysis Set

The MRD evaluable analysis set is a subset of the full analysis set, which excludes subjects who don't have baseline MRD sample or don't have post-baseline MRD assessment due to technical issues.

6.5 12-month Landmark MRD Analysis Set

The 12-month landmark MRD analysis set is a subset of the full analysis set, which excludes subjects who do not have the opportunity to have MRD sample collected at month 12. The subjects who do not have the opportunity to have MRD sample collected at month 12 are defined as subjects who ended the treatment prior to month 12.

7. Planned Analyses

CCI

CCI

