7.3.21.2 Bone Marrow Sample Evaluation Including FISH and MRD[-]CR Assessment

A baseline bone marrow sample (aspirate slides and/or biopsy) will be collected prior to first dose and will be used to confirm the diagnosis and quantify the percent (%) of myeloma cell involvement. Biopsy or aspirate slides obtained as standard of care may be used as baseline if taken within 45 days prior to randomization and are sent to the central laboratory for processing. The priority of bone marrow aspirate testing at screening (prior to dosing at cycle 1 day 1) is MRD NGS, FISH, cytomorphology, pharmacogenetics, and biomarker bone marrow aspirate. All other bone marrow aspirate assessments include MRD NGS, cytomorphology, and pharmacogenetics.

Additional bone marrow aspirate will be obtained as clinically indicated to confirm a response of CR. In addition, a bone marrow aspirate will be obtained for MRD assessment at all of the following time points:

- at a fixed, landmark analysis at 12 months (\pm 4 weeks)

- 12 months calculated from baseline (cycle 1 day 1)
- this sample is collected from subjects who have not had confirmed disease progression
- if subject reached CR prior to the 12 month landmark and the CR sample was taken within 4 months, no additional sample is required, unless clinically indicated
- when a subject reaches CR and did not have a bone marrow aspirate sample taken for MRD analysis within the past 4 months, unless there is a clinical reason to repeat the assessment
 - this sample may be collected/saved at the same time when the cytomorphology sample is collected for the confirmation of CR (per IMWG-URC criteria described in protocol [Appendix M](#))
- at 24 months (\pm 4 weeks) for all subjects that have reached a CR (at any time prior to the 24 month timepoint) and have not had an MRD assessment within the past 4 months, unless there is a clinical reason to repeat the assessment
 - 24 months is calculated from baseline (cycle 1 day 1)
 - this sample is collected from all subjects who reached CR at any time prior to the 24 month timepoint and are still receiving treatment or have not progressed and still attend site for disease assessment visits

Samples for MRD analysis are not collected from subjects who have PD confirmed or have withdrawn consent related to this study assessment. **Samples for MRD analysis are not required** [REDACTED].

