Last Known Alive Date

Last known alive date is the latest date of the following dates before death date:

- Date of Randomization on Subject Enrollment CRF
- Date First Taken, Date Last Taken on Concomitant Medications CRF
- Date Performed on ECOG Performance Status, Vital Signs, Echocardiogram, Electrocardiogram, Transfusions, Surgery, Procedure CRFs
- Admission Date, Discharge Date on Hospitalizations, CRF Date of Examination on Physical Measurement CRF
- Date Collected on Reproductive Status and Pregnancy Test (Local Lab), Chemistry (Local Lab), Hematology (Local Lab), Coagulation (Local Lab) CRFs and in central lab data
- Start Date, Stop Date on Investigational Product Administration CRF
- Date Started and Date Ended or Resulted in Death on Events CRF
- Start date, Stop date on Concurrent Radiotherapy, Anti-Myeloma / Anti-Cancer Therapies
- Subject Status Date if status is Alive on Survival Status CRF
- Assessment Date on Skeletal Survey and Plasmacytoma Assessment CRF
- Date of Clinical Outcome Assessment

Minimal Residual Disease Negative-Complete Response (MRD[-]CR)

MRD[-]CR is defined as achievement of CR (includes sCR) per International Myeloma Working Group-Uniform Response Criteria (IMWG-URC) and MRD[-] status as assessed by NGS (at a 10^{-5} level) **at 12 months landmark.**

MRD[-]CR rate is defined as the proportion of subjects achieving MRD[-]CR at 12 months landmark.

Sustained MRD[-]CR is defined as maintaining MRD[-]CR for 12 months or more after achieving MRD[-]CR status.

Sustained MRD[-]CR rate is defined as the proportion of subjects achieving sustained MRD[-]CR.

MRD[-] rate is defined as the proportion of subjects that achieved MRD[-] status as assessed by NGS (at a 10^{-5} level) at 12 months landmark.

12-month landmark is defined as 12 months (-4 months / +1 month).

Onyx Response Computational Assessment (ORCA)

Responses that are derived using ORCA will be based on the International Myeloma Working Group Uniform Response Criteria (Durie et al. 2006, with corrections, Rajkumar et al. 2011, Kumar et al. 2016) (IMWG-URC). The detailed algorithm is documented in a separate document “SPECIFICATIONS FOR ONYX RESPONSE COMPUTATIONAL ASSESSMENT (ORCA) BASED ON IMWG UNIFORM RESPONSE CRITERIA”.

Overall Response Rate (ORR)

ORR is the proportion of subjects whose best overall response is PR, VGPR, CR, or sCR.

Overall Survival (OS)

OS time in months will be calculated from time of randomization until death due to any cause:

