9.5.2 Analyses of Secondary Efficacy Endpoint(s)

Key secondary endpoints

If PFS is significant, the key secondary endpoints will be tested by sequential testing in the order of ORR, MRD[-]CR rate by NGS, and OS.

The analysis for ORR will be done if the primary analysis of PFS reaches statistical significance. **Subsequently, the analysis of MRD[-]CR rate will be done if ORR analysis reaches statistical significance.**

The inferential comparison between treatment groups for both the ORR and MRD[-]CR will be made using the Cochran Mantel Haenszel chi-square test controlling for the randomization stratification factors per IxRS. The ORR/MRD[-]CR will be calculated by treatment group and the associated 95% CI will be estimated using the Clopper-Pearson method. An estimate of the common odds ratio (95% CI) will be provided as a measure of the relative treatment effect. The odds ratio (and 95% CI) will be estimated using the Mantel-Haenszel method. The Kd arm will serve as the reference treatment group in the calculation of the odds ratio. The primary analysis of ORR will be based on IRC assessed outcomes. The analyses based on investigator-assessed and ORCA will serve as supportive analyses. Similarly, the CR portion of the MRD[-]CR endpoint will be based on IRC assessments. **The MRD assessment at month 12 is required for all subjects regardless of response. The subjects, who have progressed, might have**

withdrawn consent or stopped the study for other reasons prior to this time point, will be assessed as MRD positive and the reasons for not having an assessment will be summarized.

For subgroups listed in [section 4](#), odds ratio (with 95% CI) will be provided for ORR and MRD[-]CR rate between the treatment groups. A treatment-by-subgroup interaction test **may** be provided using a logistic regression model stratified by the stratification factors.

Overall survival will be analyzed using the same method as described for the PFS endpoints after PFS, ORR, MRD[-]CR all reach statistical significance. In the case that the PFS results are not statistically significant at the primary PFS analysis, the sponsor may stop the study and if so, the subjects will not be followed for OS any further.

Subgroup analysis for OS will be performed using the same method described for PFS as appropriate. If there is evidence to support non-proportional hazards, a piecewise proportional hazard model may be explored as described for PFS.

Other secondary endpoints

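### The SAP's 12-month landmark MRD set drops everyone off treatment before month 12, contrary to the protocol's sampling rule and the SAP's own landmark window

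*SAP*

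**What the plan says.** SAP 6.5 describes a subset of the full analysis set "which excludes subjects who do not have the opportunity to have MRD sample collected at month 12", and adds that such subjects "are defined as subjects who ended the treatment prior to month 12". No reason for ending treatment is distinguished.

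Other places bear on who can be sampled and how subjects without a sample are handled:

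- **Protocol 7.3.21.2**, on the 12-month landmark aspirate: "this sample is collected from subjects who have not had confirmed disease progression". The same section closes with: "Samples for MRD analysis are not collected from subjects who have PD confirmed or have withdrawn consent related to this study assessment". Ending treatment is not among the reasons. Its 24-month item expressly includes subjects who are off treatment, provided they have not progressed and still attend disease assessment visits.
- **Protocol Table 12**, footnote a: subjects who stop treatment before progression but remain on study continue disease assessments every 28 ± 7 days until progression.
- **SAP section 5 (Definitions)**: "12-month landmark is defined as 12 months (-4 months / +1 month"), which is month 8 to month 13.
- **SAP 9.5.2**: "The MRD assessment at month 12 is required for all subjects regardless of response". Subjects who progressed, withdrew consent or left the study earlier "will be assessed as MRD positive and the reasons for not having an assessment will be summarized".
- **SAP 6.1 and 9.5**: the primary and key secondary endpoints, including MRD[-]CR, are analysed on the full analysis set. Table 3 names only the MRD evaluable set (6.4) as an alternative population for MRD[-]CR.

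**The concern.** Opportunity to be sampled and being on treatment are different things, and 6.5 treats them as one. Two consequences follow.

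First, the set loses subjects it should keep. Someone who stops both drugs for toxicity at month 6 without progressing can still be sampled at month 12. Someone in CR who is sampled at month 9 and stops at month 11 already has a sample inside the SAP's window. Under protocol 7.3.21.2 that subject needs no further one, because a CR sample taken within the preceding 4 months suffices. Both are excluded.

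Second, membership depends on what happened after randomization. Treatment ends mainly through progression, death or toxicity, and their frequency can differ between arms. The rule also bites unevenly. Under protocol 6.2.1.2 and 6.2.2.2 a subject counts as on treatment while receiving either carfilzomib or daratumumab. A KdD subject who stops carfilzomib and continues daratumumab stays in the set, but a Kd subject who stops carfilzomib leaves it. An MRD rate computed on the set would describe those still on treatment in each arm, not the randomized groups.

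**Working it through.** **The plan's figures.** The documents give no size, rate or power for the landmark set, so there is nothing to reproduce for it. The illustration borrows the design HR of 0.6 (protocol 10.2, SAP 3.2). With 188 events, 2:1 allocation and 1-sided 0.025, √(188 × 2/9) = 6.464. Power is Φ(6.464 × 0.511 − 1.96) = 0.910 and the minimum detectable HR is exp(−1.96/6.464) = 0.738. Both agree with the plan.

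**The rules side by side**

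| Subject at month 12 | Protocol 7.3.21.2 | SAP 6.5 |
|---|---|---|
| On treatment, no PD | sampled | in |
| Off treatment, no PD, consent in place | sampled | out |
| CR sample at month 9, stopped at month 11, no PD | existing sample suffices | out |
| Confirmed PD, treatment ended | not sampled | out |

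Rows 2 and 3 are the conflict.

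**Calendar time is not the reason.** Accrual is estimated at 11 months (protocol 3.5.1) and the primary analysis at about 27 months after first enrolment (3.5.2). The last subject would have about 27 − 11 = 16 months. On that timing the data cutoff denies nobody a month-12 sample.

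**Illustrative size.** Inputs:

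- Kd median PFS 18.7 months, from the reference Kd trial (protocol 2.5.4), because this trial's own control assumption is redacted. Range taken: 15 to 22 months.
- HR 0.6 and exponential PFS.
- Progression or death as the only cause of ending treatment.
- No excluded subject was MRD[-]CR.
- MRD[-]CR rates are assumptions.

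Formulas: share of Kd kept = 0.5^(12/median); share of KdD kept = (share of Kd kept)^0.6; apparent rate = true rate ÷ share kept. For a true ratio of 2.0, apparent ratio = 2.0 × Kd kept ÷ KdD kept.

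| Kd median (months) | Kd removed | KdD removed | Left (Kd / KdD) | Apparent ratio |
|---|---|---|---|---|
| 15 | 43% | 28% | 86 / 215 | 2 × 0.574/0.717 = 1.60 |
| 18.7 | 36% | 23% | 96 / 230 | 2 × 0.641/0.766 = 1.67 |
| 22 | 31% | 20% | 103 / 239 | 2 × 0.685/0.797 = 1.72 |

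At 18.7 months, true rates of 10% (KdD) and 5% (Kd) would appear as 0.10/0.766 = 13.1% and 0.05/0.641 = 7.8%. True rates of 10% in both arms would appear as 13.1% (KdD) and 15.6% (Kd). The denominators alone create that difference.

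**Subjects wrongly dropped.** If a further 5% to 15% of progression-free subjects stopped for other reasons (assumption), the loss would be 0.05 × 96 to 0.15 × 96, about 5 to 14 Kd subjects. For KdD it would be 0.05 × 230 to 0.15 × 230, about 11 to 34 subjects. The protocol's rule would still sample them.

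**The case against.** **No visible inference rests on the set.** This stands. The alpha-controlled test uses the full analysis set with early failures scored MRD positive, and Table 3 does not cite 6.5. A reader might infer that the MRD[-]CR test or the testing hierarchy is biased. The documents do not support that. Parts of the SAP are redacted, so a use cannot be excluded, but none can be asserted.

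**The set may serve another purpose.** The SAP's references include work on survival by tumour response and on guarantee-time bias that the visible text never cites. That would fit a landmark analysis of outcome by MRD status, where conditioning on reaching the landmark is deliberate. This is plausible but unstated, and such an analysis still gives no reason to drop progression-free subjects with valid samples because they stopped treatment.

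**The protocol is not wholly clear.** Section 7.2.3 lists the MRD aspirate under the treatment period. Section 7.2.4 lists only serum and urine tests for subjects who stop before progression. The SAP was written to Amendment 4, the protocol available is Amendment 6, and Amendment 5 changed marrow sampling. These points soften the conflict, but the explicit list of non-sampling reasons, Table 12 and SAP 9.5.2 point the other way.

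**A subset may exclude subjects whom 9.5.2 counts.** True; that alone is no contradiction. The fault is in how opportunity is defined.

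**The size is uncertain.** A reader might instead use the reference Kd arm's median of 48 weeks on carfilzomib. With 0.6 as a stopping-hazard ratio, that gives 53% of Kd and 36% of KdD removed and an apparent ratio of 1.48. The documents do not support that as the estimate. It borrows carfilzomib exposure from another trial, applies a PFS hazard ratio to stopping, and ignores that KdD subjects remain on treatment with daratumumab alone. At a stopping ratio of 0.8 the apparent ratio is about 1.72, and at 1.0 it stays 2.0.

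**Conclusion.** The definition in SAP 6.5 is wrong as written. It conflicts with the protocol's sampling rule and with the SAP's month 8 to 13 window, and it drops progression-free subjects who are off treatment, including some who may have valid landmark samples.

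The consequence is limited and conditional. If between-arm MRD rates were reported on this set, both would be inflated to the extent that excluded subjects have lower MRD[-]CR rates than those kept, and the comparison would shift wherever the arms lose different shares. Under the stated assumptions about 36% of Kd and 23% of KdD would go (43%/28% to 31%/20% for Kd medians of 15 to 22 months), and a true ratio of 2.0 would read about 1.67 (1.60 to 1.72). A reader might expect the set to flatter KdD; here the shift is against it, and the direction is not fixed in general. The key secondary test and the type I error are unaffected.

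**What to change.** In SAP 6.5:

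1. Replace the end-of-treatment criterion with the protocol's sampling rule. Exclude a subject only for confirmed progression, death or withdrawn consent before the landmark, and only if there is no MRD sample in the month 8 to 13 window.
2. Keep anyone with a sample in that window, whatever the treatment status.
3. State that the set is supplementary, and that between-arm MRD rates are taken from the full analysis set with early failures scored MRD positive as in 9.5.2. This is needed because the aligned set still removes early progressions and deaths, so the distortion illustrated above would remain in any rate comparison on it.

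If the set has no purpose the sponsor can name, delete it. Redefining it by calendar opportunity would add little: with about 16 months of follow-up for the last subject, it would nearly reproduce the full analysis set.

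The cost is a minor SAP edit and a small programming change to the set's derivation. Data collection does not change.
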